game will be adjusted according to the information provided during the assessment so that the user needs to move their body accordingly in different directions without losing their balance. This equipment is specially designed for rehabilitation for people with movement disorders, hence unlike the commercial games, there are no flashing lights or sudden noises during the games. To our best knowledge, there has been no study published using Tymo as an intervention for training trunk control in children with CP.

c) Aims and Hypotheses to be Tested:

Conducting a pilot single-blinded randomised controlled trial (RCT), the overall objective is to investigate the effect of a 6-week training programme using an interactive computer play training tool on the segmental trunk control, sitting and/or standing balance and gross motor function in children with CP.

The hypotheses to be tested are:

- (1) That after 6 weeks of training using the interactive computer play training tool, Tymo, the children with CP will show significant improvement in their segmental trunk control as demonstrated in the SATCo.
- (2) That after 6 weeks of training using the interactive computer play training tool, Tymo, the children with CP will show significant improvement in their balance in sitting and/or standing positions as demonstrated in the PRT.
- (3) That after 6 weeks of training using the interactive computer play training tool, Tymo, the children with CP will show significant improvement in gross motor activities as demonstrated in the GMFM 88.
- (4) That after 6 weeks of training using the interactive computer play training tool, Tymo, children with CP, who are able to ambulate independently with a walking aid, will show a significant improvement in the distance covered in 2 minutes.

d) Plan of Investigation:

(i) Subjects

Selection criteria:

- (1) Children with a diagnosis of CP will be of GMFCS levels III to IV, who in general, require walking aid (level III) during ambulation and with limited walking ability (level IV).^[4] Aiming to achieve a higher homogeneity of the recruited children, for those with level III, only those requiring physical assistance to climb stairs will be recruited and so it is believed that only those with lower motor ability, i.e. similar to level IV, will be included.
- (2) Children, with non-CP physical disabilities, will have similar gross motor function as in (1).
- (3) Aged from 6 to 12 years old and

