- (4) Able to follow instructions to interact in simple computer games

Sample size calculation: There is no previous published study using the primary outcome measure (see below under Methods) to examine the effect of the ICP on trunk control in this population group, hence, no sample size calculation is possible based on previous data. Thus it is estimated that 20 children with 10 children in each arm for this pilot RCT is appropriate and feasible. The sample size will be the largest among the previous studies in this area.

Exclusion criteria:

- (1) Children with epilepsy/ seizures that could be elicited by flashing lights or sudden loud noises from computer screens

(ii) Methods

Outcome measures (OM) used in this proposal include:

Primary study outcome:

- (1) Segmental Assessment on Trunk control (SATCo)^[8] assessment on the child's segmental trunk control by progressively reducing the trunk support from the shoulder girdle to assess the

head control, through support at the axillae (upper thoracic), inferior scapula (mid-thoracic), lower ribs (lower thoracic), below ribs (upper lumbar), pelvis (lower lumbar) and no support to measure full trunk control.^[8] The trunk control is tested under 3 different conditions in sitting: to maintain the posture (static control), during voluntary head movements (active control) and recovery of trunk control after a disturbance of balance by a nudge (reactive control).^[8]

Secondary study outcomes:

(2) Pediatric Reach Test (PRT)^[22] assessment on balance in sitting and standing positions. The distance how far the child can reach forward, to right and to left will be measured in sitting and standing. High construct validity has been shown between the PRT in standing and a laboratory test of steadiness in quiet stance ($r= 0.79$) and age ($r= 0.83$) in a group of 19 typically developing children. High construct validity has also been shown between the total PRT score and GMFCS level ($r= 0.88$) among a sample of 10 children with cerebral palsy. Test-retest reliability and inter-tester reliability with children with cerebral palsy was moderate to high (intraclass correlation coefficients= 0.54 to 0.88 and 0.50 to 0.93 respectively)^[22] and

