(3) Gross Motor Function Measure 88 (GMFM 88)^[23] assessment on general gross motor function in various positions including lying, sitting, 4-point kneeling, high kneeling and standing. The intra- and inter-rater reliability of the GMFM 88 have been shown to be very high (ICC= 0.99 in both cases).^[23]

(4) 2-minute walk test^[24] distance covered in a period of 2 minutes with self-chosen comfortable speed will be measured. The walk test has been shown to have high test-retest, intra- and inter-rater reliability.^[24]

(5) The height and weight of the children

(iii) Study design

20 children with CP or similar physical disabilities will be recruited from 2 special schools for children with physical disabilities in Hong Kong for this pilot RCT (see 'Existing facilities' for details). Informed consent will be sought from the parents or guardians before the study will commence. After the initial assessment, all study children will be randomly allocated into a control group or treatment group (10 children in each arm) using a 'draw card from the hat'. The randomization will be separately done in each school so as to take into account the heterogeneity of the children and treatment regime in each school. The children in the treatment group will receive training on their trunk control using the Tymo in sitting 4 times per week for 20 minutes per session. The treatment will last for 6 weeks. All study children will continue their usual therapies at school but will be asked to stop playing any interactive computer play, which is designed to train balance such as Nintendo Wii balance board, during the study period. As there is no strong research evidence that commercial computer games are effective in improving the balance for children with CP and this type of commercial computer play is not a routine training exercises for balance in the treatment sessions at the schools, it is believed that discontinuing this type of 'training' for 6 weeks would not cause detrimental effect on the balance of the study children.

All the assessment will be carried out by a blinded assessor (PA), who is not aware of the group allocation of the children. All the children will be assessed at the beginning, and 3, 6 and 12 weeks after the commencement of the intervention. The last assessment aims to examine the medium-term effect on their trunk control post-intervention.

Intervention:

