All participating children will be calibrated using the Tymo in a static sitting position in each treatment session by the research staff. Force and weight distribution will be calibrated by asking the child to move the trunk forward, backward and sideways as far as s/he can. The amplitude of the force and weight distribution between the two sides of the body will be recorded. These

information will be used to set up the Tymo as a balance training module (the intervention) by the software, in which the child will move the trunk forward, backward and sideways to participate in a computer game in a sitting position (Tables 1 and 2). The child will be allowed to choose which game they want in each treatment session and they have to stay on the same game for at least 10 minutes before changing to another game. In other words, the child will have a maximal choice of 2 computer games in each treatment session. All children will start at a medium level of difficulty. Only if the child is unable to score any point in 3 trials in a row, the difficulty level will be reduced to one level down. Similarly, if the child scores full points in 3 trials in a row, the difficulty level will be increased to one level up. The progression of the intervention will then be closely monitored by the research staff. A logbook will be used for each child to record the level of difficulty in each treatment session, the number of treatment sessions, duration of each session and general comments on the child in each session during the intervention phase. The intervention will be supervised by a research assistant, who will be employed for the study.

(iv) Data processing and analysis

Statistical analyses: SPSS for Windows (version 20) will be used to analyse the results. Mann Whitney U test will be used to compare the results of the OM(1) between the intervention and control groups and independent t-test for OM(2) to OM(5). The statistical significance level is set at $p < 0.05$.

[Word Court: 3814]

e) Existing Facilities:

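### Height and weight are tested between arms as a secondary outcome with no growth hypothesis, while reach and walk distances are compared without using the baseline scores already collected

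*Combined protocol and SAP*

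**What the plan says.** Section d)(ii) opens its list with "Outcome measures (OM) used in this proposal include". Item (5), under the secondary outcomes, is "The height and weight of the children". Section d)(iv) assigns the Mann-Whitney test to OM(1) and "independent t-test for OM(2) to OM(5"), so height and weight are included. It adds "The statistical significance level is set at $p < 0.05" and names no covariate.

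The four hypotheses in section c) concern SATCo, PRT, GMFM 88 and 2-minute walk distance. The first, for example, expects "significant improvement in their segmental trunk control as demonstrated in the SATCo". None mentions height, weight or growth.

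PRT and the walk test are both recorded as distances. Section d)(iii) schedules assessments at baseline and at 3, 6 and 12 weeks, so a baseline value of each outcome will exist. The size is "20 children with 10 children in each arm for this pilot RCT is appropriate and feasible", and the protocol says that "no sample size calculation is possible based on previous data".

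**The concern.** There are two linked faults.

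- **A test without a question.** The documents give no reason why six weeks of seated 20-minute sessions would change height or weight. If they do not, the only significant result that OM(5) can produce is a false one, and it would be reported beside the real secondary outcomes.
- **Information left unused.** Reach and walk distance will vary widely between children before any training. A two-sample t-test on follow-up values leaves all of that variation in the error term. The sample was fixed by feasibility, so there is no spare power to absorb the loss.

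The first fault affects how the results are read. The second affects how much the trial can learn about hypotheses 2 and 4.

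**Working it through.** The plan states no power, effect size or SD, so there is no figure of its own to reproduce.

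**Inputs from the protocol:** 10 per arm (d)(i)); significance level 0.05 (d)(iv)), taken as two-sided because sidedness is not stated; PRT test-retest coefficients in children with cerebral palsy of 0.54 to 0.88 (d)(ii)).

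**Assumptions:** a 0.8 SD difference for illustration; height-weight correlation 0.5-0.9; baseline-to-follow-up correlation r_b equal to the test-retest range; height-reach correlation r_h of 0.3-0.7, the same at baseline and follow-up.

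**Step 1: false positives on OM(5), one visit.** If the two tests were independent, the chance of at least one p < 0.05 would be 1 − 0.95² = 9.75%. Height and weight are correlated, which lowers it. Simulating two t-tests with 10 per arm gives about 9%, 8% and 7% at height-weight correlations of 0.5, 0.7 and 0.9.

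**Step 2: planned t-test.** The noncentrality is 0.8/√(2/10) = 0.8/0.447 = 1.79 on 18 df. Power is 40%.

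**Step 3: ANCOVA on the baseline score.** Residual variance is 1 − r_b², noncentrality is 0.8/√[(1 − r_b²)(2/10)], and df = 17.

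| r_b | Residual variance | Noncentrality | Power |
|---|---|---|---|
| 0.54 | 1 − 0.2916 = 0.708 | 2.13 | 52% |
| 0.71 (midpoint) | 1 − 0.5041 = 0.496 | 2.54 | 67% |
| 0.88 | 1 − 0.7744 = 0.226 | 3.77 | 94% |

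**Step 4: adding baseline height (PRT only, 16 df).** With height correlated r_h with both baseline and follow-up reach, R² = (r_b² + r_h² − 2·r_b·r_h²)/(1 − r_h²). For r_b = 0.54 and r_h = 0.7, R² = (0.2916 + 0.49 − 0.5292)/0.51 = 0.495. The residual is 0.505 against 0.708, a further cut of 29%.

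| r_h | Further cut at r_b = 0.54 | Further cut at r_b = 0.88 |
|---|---|---|
| 0.3 | 3% | 0.6% |
| 0.5 | 10% | 2% |
| 0.7 | 29% | 6% |

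In power terms, for r_h of 0.5-0.7, height takes 52% to 56-66% at r_b = 0.54, and barely moves 94% (about 95%) at r_b = 0.88.

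The 29% is an extreme corner. A measure with reliability 0.54 cannot correlate above √0.54 = 0.73 with anything, and r_h = 0.7 would make height 0.49/0.54 = 91% of the true-score variance.

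**The case against.** **Height and weight may be meant as descriptors, and nobody would take a chance difference for a treatment effect.** The second half is largely right. A spurious result here supports no hypothesis and leaves the error rates of the other tests unchanged, so the harm is small. The text nevertheless makes them outcomes with a prescribed test.

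**The unadjusted t-test is valid under randomisation.** This stands. The loss is precision and exposure to chance imbalance, not bias.

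**The comparison may be of change scores.** The hypotheses speak of improvement, and d)(iv) does not say which values are compared. For change scores the variance is 2(1 − r_b), or 0.92 to 0.24 over the same range, giving power of about 42% to 93%. ANCOVA would still have the smaller variance, by the factor (1 + r_b)/2 = 0.77 to 0.94, but the gain would be much less than in step 3. The plan must say which is intended.

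**A reader might infer that reach and walk distance are known to depend on body size, and that omitting height is the main loss.** The documents do not support this. The only related figure is a correlation of standing reach with age, not height: "and age ($r= 0.83$) in a group of 19 typically developing children". Squaring it (0.69) describes age in healthy children, not height in children at GMFCS III-IV. The next sentence of the protocol reports 0.88 between total PRT score and GMFCS level in 10 children with cerebral palsy, which points to motor severity. For the walk test nothing is documented. Height alone, against no adjustment, would raise power from 40% to 50-66% at an assumed r_h of 0.5-0.7, but much of that gain comes from the baseline score anyway.

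**Conclusion.** The point holds as a minor one on secondary outcomes of a pilot. That OM(5) is tested without a hypothesis follows from the text alone; the 7-9% chance of a spurious result per visit depends on the assumed height-weight correlation and on no effect on growth.

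The precision loss is real if follow-up values are compared as they stand. Its size, 40% against about 52-94% power at 0.8 SD, depends on test-retest coefficients standing in for the correlation between baseline and later visits. A longer interval could lower that correlation, so the upper end may be optimistic. The figures apply to PRT with all 20 children followed. They do not carry over to the walk test, for which no coefficient is given and which hypothesis 4 limits to children who walk with an aid, so the arms are probably smaller than 10.

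The baseline score is the main covariate. Height is a possible small addition for PRT, with an extra gain from negligible to about 29% of residual variance under assumed correlations of 0.3-0.7.

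**What to change.** - In d)(iv), limit the t-test sentence to OM(2) to OM(4). Take height and weight out of the outcome list and report them at baseline by arm, without a test.
- State that PRT and 2-minute walk distance are compared between arms by ANCOVA with the baseline score of the same measure as covariate, and name the visit to which each comparison applies.
- If wanted, pre-specify baseline height as a second covariate for PRT only. Decide before data are seen, because choosing covariates afterwards with 20 children invites selective analysis. Do not add height to the walk analysis.

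The cost is a few sentences and no new data. The baseline score uses one degree of freedom per analysis (18 to 17 with all 20 children), and height would use a second (16).

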Both the PA and co-applicant are very experienced paediatric physiotherapists with over 20 years of experience in managing young children with movement disorders. The mother institution of the PA is the only University in Hong Kong running the undergraduate degree in Physiotherapy and the Department of Rehabilitation Sciences at the Hong Kong Polytechnic University has abundant experiences in conducting research studies on individuals with movement disorders. Space will be provided for data storage (both hard and soft data) and statistical software will be provided for the present study. The co-applicant is the developer of the SATCo and is active in conducting research studies with collaborating researchers in USA and Denmark in examining trunk control in children with CP.

The Medical Technologies Ltd is the sole agent in Asia, which manages the Tymo Therapy plate. The agent will provide training and support in using the Tymo Therapy plate to all relevant personnel in this study in Hong Kong, as part of their quote on the equipment.

Initial contact has been made with the physiotherapists in-charge at 3 special schools in Hong Kong, namely the John F Kennedy Centre, the Red Cross Princess Alexandra School and Pui Oi School (all are special schools for children with physical disabilities), who all show interests to participate in the study. Specifically, the study children will be recruited from the first two schools and these schools will accommodate the Tymo Therapy Plate on site during the intervention phase. The physiotherapists in-charge tentatively believed that recruitment of 20 children with CP or similar physical disabilities is feasible in the first 2 schools. In case the recruitment falls short or a substantial drop-outs during the study period, Pui Oi School would be approached for further recruitment.

f) Justification of Requirements:

Staffing- a Physiotherapist will be employed to supervise the children to carry out the ICP at respective schools. Salary for this personnel is set as point 19 (median point of Physiotherapist II) of MPS, i.e. \$32,560 per month + \$1,500 MPF per month for 6 months= \$204,360 because the personnel is required to have experience in managing paediatric clients with physical disabilities and has

understanding of postural control in children.

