The present study is designed to overcome these shortfalls. It is a single blinded controlled trial with 20 children with CP in each arm. The intervention, ICP is a specifically designed balance training tool for rehabilitation (www.tyromotion.com). One of the outcome measures used is an assessment of segmental trunk control, which will capture subtle changes in trunk control in different segments, instead of considering the whole trunk as one unit. The targeted children with CP are relatively homogeneous. It is the first of the series in using ICP for children with movement disorders. If the intervention is proven to be effective, ICP may be an adjunct to the conventional Physiotherapy to children with movement disorders. With the future Hong Kong Children's Hospital in mind, the ICP may be an essential piece of equipment in the rehabilitation program in the wards. Furthermore, future studies on different population groups with movement disorders, such as Developmental Coordination Disorders and children with preterm birth, will be conducted using the ICP.

Results of the present study will be presented in local and overseas conferences, e.g. Hong Kong Physiotherapy Association conference, American Academy of Cerebral Palsy and Developmental Medicine conference etc. Results will also be submitted for publication in high ranking journals such as Developmental Medicine and Child Neurology (impact factor 3.292) and Journal of Physiotherapy

(impact factor 2.894).

h) Key References:

1. Oskoui, M., et al., *An update on the prevalence of cerebral palsy: a systematic review and meta-analysis*. *Developmental Medicine and Child Neurology*, 2013. **55**(6): p. 509-519.
2. Yam, W., et al., *Prevalence study of cerebral palsy in Hong Kong children*. *Hong Kong Medical Journal*, 2006. **12**(3): p. 180-184.
3. Mutch, L., et al., *Cerebral palsy epidemiology: where are we now and where are we going?* *Developmental Medicine & Child Neurology*, 1992. **34**: p. 547-551.
4. Palisano, R.J., et al., *Development and reliability of a system to classify gross motor function in children with cerebral palsy*. *Developmental Medicine & Child Neurology*, 1997. **39**: p. 214–23.
5. Carlberg, E.B. and M. Hadders-Algra, *Postural control in sitting children with cerebral palsy*, in *Postural Control: a Key Issue in Developmental Disorders*, M. Hadders-Algra and E.B. Carlberg, Editors. 2008, Mac Keith: London. p. 74-96.

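### Randomisation is stratified by school but the planned tests pool the schools, so power is lost if school predicts the outcome

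*Combined protocol and SAP*

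**What the plan says.** Section d)(iii) of the combined protocol and SAP plans that "20 children with CP or similar physical disabilities will be recruited from 2 special schools", with 10 children per arm allocated by drawing cards. It makes school a randomisation stratum and gives the reason: "The randomization will be separately done in each school so as to take into account the heterogeneity of the children and treatment regime". All children keep their usual school therapies during the trial. The split between arms within a school is not stated.

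Section d)(iv) holds the whole analysis plan. For the primary outcome, "Mann Whitney U test will be used to compare the results of the OM(1) between the intervention and control groups". OM(2) to OM(5) are compared by independent t-tests, and significance is set at p < 0.05. No school term, stratified test or covariate appears there or elsewhere. The word used for what is compared is simply results, so it is open whether final values or changes from baseline are meant.

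Three other places bear on the point. Section e) allows a third school: "In case the recruitment falls short or a substantial drop-outs during the study period". Hypothesis 4 in section c) limits the walking outcome to children "who are able to ambulate independently with a walking aid", so that comparison will have fewer than 20 children. Section g) states: "The targeted children with CP are relatively homogeneous".

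**The concern.** Stratifying the draw helps to balance the arms over schools. It improves precision only if the analysis also uses school. A pooled test counts the difference between schools as random error. If arms are near-equal within each school, the treatment comparison contains almost none of that difference, yet the estimated error does; the test is then conservative and loses power. If arms are not equal within school, the type I error stays near 5%, but the school difference adds real noise to the comparison and power is again lost.

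The trial has 10 children per arm and no power calculation, so precision is scarce. The protocol itself names school heterogeneity as the reason for its design. If that reason holds for the outcomes, the planned tests discard the benefit, including for the primary outcome.

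**Working it through.** **Inputs from the documents.** Two schools, 10 per arm, p < 0.05 (taken as two-sided). Section g) speaks of 20 per arm; sections d)(i) and d)(iii) say 10, and 10 is used here. The plan states no power figure, so there is none to reproduce.

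**Assumed inputs.** 5+5 children per school; normal outcomes with within-school SD 1; effect of 1.3 SD or 0.8 SD; school gap g of 0, 0.5, 1.0 or 1.5 SD. For scale, 10 per arm gives 80% power at an effect of about 1.32 SD. A gap of g between two equal schools explains (g²/4)/(1 + g²/4) of the outcome variance: 0, 6, 20 and 36%.

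**Step 1: the mechanism for the t-test.** With 5+5 per school, the arm difference has variance 1/10 + 1/10 = 0.2 whatever the gap. The within-arm sum of squares has expectation 18 + 20 × (g/2)² = 18 + 5g² on 18 degrees of freedom. The pooled variance is therefore overstated on average by the factor 1 + 5g²/18, and the critical value 2.101 in effect becomes 2.101 × √(1 + 5g²/18).

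| Gap (SD) | Factor | Effective critical value | Type I error, t with 18 df |
|---|---|---|---|
| 0 | 1.000 | 2.101 | 5.0% |
| 0.5 | 1.069 | 2.173 | 4.3% |
| 1.0 | 1.278 | 2.375 | 2.9% |
| 1.5 | 1.625 | 2.678 | 1.5% |

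**Step 2: t-test simulation** (40,000 trials per setting, Monte Carlo SE at most 0.25 points). It agrees with step 1.

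| Gap (SD) | Type I, pooled | Type I, with school | Power at 1.3 SD, pooled | with school | Power at 0.8 SD, pooled | with school |
|---|---|---|---|---|---|---|
| 0 | 4.9% | 4.9% | 78.7% | 78.5% | 39.9% | 39.7% |
| 0.5 | 4.4% | 5.1% | 76.4% | 78.3% | 37.3% | 39.7% |
| 1.0 | 3.0% | 5.2% | 70.1% | 78.3% | 30.2% | 39.3% |
| 1.5 | 1.4% | 4.8% | 59.7% | 78.1% | 21.6% | 39.2% |

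**Step 3: SATCo** (outcome cut into 7 ordered categories, an assumption; p-values by enumeration or relabelling; 6,000 trials, SE at most 0.7 points; power at 1.3 SD).

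| Gap (SD) | Mann-Whitney type I | Mann-Whitney power | van Elteren power | Mann-Whitney statistic permuted within school, power |
|---|---|---|---|---|
| 0 | 4.2% | 72.8% | 70.8% | 72.3% |
| 0.5 | 4.0% | 71.2% | 71.5% | 72.5% |
| 1.0 | 2.8% | 65.7% | 72.6% | 73.4% |
| 1.5 | 1.2% | 52.3% | 71.1% | 72.2% |

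At a 1.0 SD gap the gain is 73.4 − 65.7 = 7.7 points with within-school permutation and 72.6 − 65.7 = 6.9 with van Elteren. Both stratified tests keep type I error at 4.1-4.8%.

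**Step 4: less favourable layouts** (gaps 0 / 0.5 / 1.0 / 1.5 SD, 1.3 SD effect).

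- *10 per arm overall, unbalanced within school:* pooled t-test type I error 4.8-5.1%; power 79.0 / 75.7 / 68.9 / 58.6%, against 76.3 / 75.7 / 75.9 / 75.9% with school.
- *Three schools (4+4, 4+4, 2+2), SATCo:* Mann-Whitney 73.9 / 71.2 / 65.7 / 55.0%, against 72.9 / 71.9 / 71.9 / 70.8% permuted within school.
- *Walk test with only 2+2 walkers per school:* t-test 34.0 / 31.6 / 24.6 / 16.3%, against 32.1-32.4% with school.

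**Step 5: a second parameterisation.** With the effect set at 1.0 total SD and school explaining 20% of the variance, power is 56% pooled against 65% with school (t-test, linear model), and 52% against 61% (Mann-Whitney, van Elteren, 7 categories). Splits of 7+7/3+3 and 8+8/2+2 give the same pattern.

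**The case against.** The strongest objection is that these losses depend on what is analysed. All hypotheses speak of improvement and every child has a baseline assessment, so change scores are a natural reading. A constant school difference in level then cancels. With an assumed 0.8 SD effect and a baseline-final correlation of 0.6 or 0.8, change-score power is 47-48% or about 76%, with or without school. This stands. But schools may also differ in change, because usual therapy continues and section d)(iii) says the regimes differ. With correlation 0.8 and a 0.5 SD school gap in change, power is 71% pooled against 76% with school. Change then has SD √(2 × 0.2) = 0.63, so that gap is 0.5/0.63 = 0.79 SD of change. No document says how large such a gap would be.

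A related objection is that baseline is the bigger lever. At a 1.0 SD level gap and a 0.8 SD effect, adding school to final scores lifts power from 30% to 40%. Using baseline without school gives 47-52% (correlation 0.6) or 76-78% (0.8). That is a fair reason to settle the final-or-change question first. It is no reason to leave the stratification out.

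The gap is also unsupported by data, eligibility is narrowed for homogeneity, and at 0.5 SD the gain is only 1-2 points (0.3 for van Elteren, within simulation error). All true, and the reason the point is conditional. Finally, this is a pilot without a power target. It nevertheless tests hypotheses at p < 0.05, so the power of those tests matters.

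**Conclusion.** The concern holds as a conditional point about efficiency. The mismatch between design and analysis is certain: school is a randomisation stratum and no planned test uses it. The consequence depends on how strongly school predicts the analysed score, which the documents do not show.

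Under the assumed 5+5 layout and a 1.3 SD effect, using school gains nothing at no gap, about 1-2 points of power at 0.5 SD and about 7-8 points at 1.0 SD. If change scores are analysed, only a school difference in change counts. The treatment estimate is not biased and the false-positive rate is not raised. The change should be made, before data are seen, because choosing the adjustment afterwards would look selective.

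**What to change.** Amend section d)(iv), with one clarification in d)(iii):

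1. For OM(2) to OM(4), replace the t-tests by a linear model with treatment and school as fixed factors. OM(5) is height and weight; the same model serves if these are still to be tested.
2. For SATCo, keep the Mann-Whitney statistic but obtain its p-value by permuting group labels within school, as the children were randomised. The van Elteren test is the alternative.
3. State whether final or change scores are analysed.
4. If the third school is opened, treat it as its own stratum, provided it has children in both arms. A school with one arm only adds nothing to the stratified comparison.
5. State in d)(iii) that the card draw is balanced within each school.

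The cost is a few lines of text, no new data, and one degree of freedom with two schools or two with three. If schools do not differ (1.3 SD effect), the power cost is:

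- OM(2) and OM(3): under 1 point with balanced arms, about 3 if arms are unbalanced within school.
- SATCo: about 0.5 point with within-school permutation (about 1 with three schools), about 2 with van Elteren.
- Walk test: about 2 points if only 2+2 children per school can walk.

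The team should confirm that the named software, SPSS version 20, can run the stratified rank test, or name another program for it.

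### The draw is separated by school only and the tests are unadjusted, so chance can leave the arms uneven on motor level and short of walkers for hypothesis 4

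*Combined protocol and SAP*

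**What the plan says.** Section d)(iii) has the children, after the initial assessment, "randomly allocated into a control group or treatment group (10 children in each arm) using a 'draw card from the hat". The only separation is by school: "The randomization will be separately done in each school so as to take into account the heterogeneity of the children". The same sentence adds the schools' treatment regimes as a reason.

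On who is enrolled, criterion (1) in d)(i) says "Children with a diagnosis of CP will be of GMFCS levels III to IV". Level III is limited to children who need physical help on stairs, and "it is believed that only those with lower motor ability, i.e. similar to level IV, will be included". Criterion (2) also admits children with non-CP physical disabilities on comparable gross motor function, without stating a GMFCS level for them. Section g) concludes: "The targeted children with CP are relatively homogeneous".

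On how motor level relates to the outcomes, d)(ii) reports for the Pediatric Reach Test (PRT, secondary): "High construct validity has also been shown between the total PRT score and GMFCS level", with r = 0.88 in 10 children with CP. No such figure is given for SATCo (primary), GMFM 88 or the walk test. Hypothesis 4 in section c) covers only children who can walk independently with a walking aid.

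Section d)(iv) plans a Mann-Whitney U test for SATCo and independent t-tests for the other outcomes. It names no covariate and does not say whether final or change scores are compared.

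**The concern.** The plan separates the draw in order to handle differences between children, but school is an indirect way to do that. Motor level is the more direct source of difference, and the initial assessment comes before the draw. If the mix of levels is alike in both schools, drawing by school does nothing to balance it, and the analysis does not correct what the draw leaves.

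The background section describes level IV as limited in assisted standing, stepping and transfers, while hypothesis 4 presupposes some enrolled children who walk independently with an aid. Some spread in ability therefore remains despite the restriction on level III. With about 10 children per arm, an uneven split would shift the arm means on any outcome that follows motor level. It could also leave one arm with few children for hypothesis 4.

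**Working it through.** The plan states no figure for balance on motor level, so there is nothing to reproduce. Its sample size was set by feasibility: "Thus it is estimated that 20 children with 10 children in each arm for this pilot RCT is appropriate and feasible".

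**Inputs from the documents.** Twenty children, 10 per arm, two schools, a separate draw in each school (d)(i), d)(iii)); r = 0.88 between total PRT score and GMFCS level, n = 10 (d)(ii)); p < 0.05 (d)(iv)).

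**Assumptions, not in the documents.** Ten children per school split 5:5; k level IV children in each school; two-sided tests.

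**1. Chance of an uneven split.** The number of level IV children drawn to treatment in one school is hypergeometric (10 children, k of level IV, 5 drawn). Let X be the sum over the two schools. The arms differ by |2X − 2k|.

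For k = 5, the single-school probabilities of 0 to 5 level IV children are 1, 25, 100, 100, 25 and 1, each over 252. A difference of 4 or more means X ≤ 3 or X ≥ 7. Over 252² = 63,504, the counts for X = 0, 1, 2, 3 are 1, 50, 825 and 5,200, which sum to 6,076. So P = 2 × 6,076 / 63,504 = 0.191.

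For k = 2, the single-school probabilities are 2/9, 5/9 and 2/9. A difference of 4 needs X = 0 or X = 4, so P = 2 × (2/9)² = 0.099.

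| Level IV per school of 10 | P(difference ≥ 4) | P(difference ≥ 6) |
|---|---|---|
| 5 and 5 | 0.191 | 0.028 |
| 4 and 4 | 0.183 | 0.024 |
| 3 and 3 | 0.153 | 0.014 |
| 2 and 2 | 0.099 | 0 |
| 1 and 9 | 0 | 0 |
| 0 and 10 | 0 | 0 |

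Counting level III instead gives the same figures by symmetry. With schools of 12 and 8 and 10 level IV children in all, P(≥ 4) is 0.15 to 0.19. With no separation by school and 10 level IV children it is 0.179. The school draw therefore protects only when level nearly follows school.

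**2. Effect on an outcome related to level.** A 7 v 3 split moves the arm means apart by (0.7 − 0.3) × gap = 0.4 × gap. For an assumed III–IV gap of 1 to 2 within-level SDs, that is 0.4 to 0.8 SD on final scores with no treatment effect. In simulation at that split, the two-sided t-test rejects in about 10% (gap 1 SD) to 16% (gap 2 SD) of trials.

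Averaged over all draws with k = 5, the same simulation rejects in about 5% of trials. Balanced draws reject less often than 5%, and this offsets the uneven ones.

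**3. How far r = 0.88 reaches.** The GMFCS range of the 10 children is not given. If they were spread evenly over levels I to V, the level SD is 1.414 and the implied step per level is 0.88 / (1.414 × √(1 − 0.88²)) = 1.31 residual SDs. With an even III/IV mix, the correlation within those levels is then 0.655 / √(1 + 0.655²) = 0.55, where 0.655 is half the step. The approximate 95% interval for r itself is 0.56 to 0.97.

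**The case against.** The strongest reply is that this is a 20-child pilot with a valid draw, that level III is narrowed on purpose, and that adjusting for baseline would address the same risk without extra hats. Much of this stands. In the worst case tabulated, about 81% of draws leave the arms within two level IV children of each other, and only about 9.6% favour the treatment arm by four or more. The per-school counts and the level mix are assumed. The restriction on level III should narrow the gap, though the plan offers this as a belief, without data. If change scores are compared, much of a stable level difference cancels.

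A reader might infer more than the documents support:

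- **That the test is invalid.** It is not; the overall type I error is not inflated.
- **That all four hypotheses could agree falsely because of the draw.** A correlation with GMFCS level is given only for PRT. The background section does link severity to sitting control, but it gives no GMFCS figure for SATCo or GMFM 88.
- **That the walk test shifts along with the other outcomes.** It concerns walkers only, so an uneven draw there mainly costs numbers.
- **That r = 0.88 applies within III–IV.** It is a cited validity figure from 10 children of unstated range, and is probably weaker across two adjacent levels.
- **That GMFCS level is known for every child before the draw.** The non-CP children have no stated level.

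**Conclusion.** The point holds in limited form and is worth acting on before the first draw. Neither the draw nor the analysis deals with motor level in a sample that mixes levels III and IV. Under the assumed two schools of 10 with 2 to 5 children of one level in each, a difference of four or more level IV children arises in about 10% to 19% of draws, both directions combined, and almost never if level follows school. The harm is conditional bias and lost precision on outcomes related to motor level, smaller for change scores, and possibly too few walkers in one arm for hypothesis 4. Its size on any outcome depends on an III–IV gap that the documents do not give.

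The figures use 10 children per arm. Section g) states otherwise: "It is a single blinded controlled trial with 20 children with CP in each arm". The two statements must be reconciled. At 20 per arm (assuming two schools of 20 with 10 level IV children each), a split of 14 v 6 or worse has a probability of about 0.03.

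**What to change.** **In d)(iii).** Within each school, draw separately for children who do and do not walk independently with an aid at the initial assessment. Walking status also places the non-CP children and matches the population of hypothesis 4. Put equal numbers of treatment and control cards in each hat. Where a hat is odd, give the spare card to the opposite arm in that school's other hat. If a school's total is odd, offset it in the other school.

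**In d)(iv).** Account for the same grouping: for example, a stratified rank test (van Elteren) for SATCo, and a linear model with school, walking status and baseline score for the continuous outcomes. State whether final or change scores are compared.

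**Effect and cost.** With even hats the arms match on walking status. With one odd hat of walkers they differ by 1. With two, they differ by at most 2 (6 v 4 when there are 10 walkers, half the time if the spare cards fall independently). A 7 v 3 split on walking status cannot then occur. GMFCS level is balanced only as far as it follows walking status. The change needs one more hat per school and no new data or staff. The arms may differ by a child, all children in a hat must be assessed before it is drawn, and with about five children per hat the stratified analysis will be thin.
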